7.6.11 Vital Signs

Vital signs collected on the CRF will be provided in a listing.

7.6.12 Physical Measurements

Physical measurements will be listed by subject.

[REDACTED]

[REDACTED]

7.6.14 Pregnancy

A by-subject listing of pregnancy tests results will be provided for randomized female subjects.

7.6.15 Adverse Events By Subgroup

Overall summary of any AEs and drug-related AEs by worst CTC grade (any grade, grade 3-4, grade 5) presented by SOC/PT and for each treatment group for the following subgroups:

- Sex (Male vs. Female)
- Race
- Age (< 65 vs. 65 - < 75 vs. 75 - < 85 vs. ≥ 85 vs. ≥ 75 vs. ≥ 65)
- Region (Asia, RoW [including US/Canada, Europe])

These analyses will be conducted using the 30-day safety window only.

[REDACTED]

[REDACTED]

[REDACTED]

[REDACTED]

[REDACTED]

[REDACTED]

[REDACTED]

[REDACTED]

[REDACTED]

[REDACTED]

[REDACTED]

[REDACTED]

[REDACTED]

[REDACTED]

[REDACTED]

[REDACTED]

[REDACTED]

[REDACTED]

[REDACTED]

[REDACTED]

[REDACTED]

8 CONVENTIONS

The following conventions may be used for imputing partial dates for analyses requiring dates:

- For missing and partial adverse event onset dates, imputation will be performed using the Adverse Event Domain Requirements Specification¹⁷
- For missing and partial adverse event resolution dates, imputation will be performed as follows (these conventions may change):
 - If only the day of the month is missing, the last day of the month will be used to replace the missing day. If the imputed date is after the death date or the last known alive date, then the latest known alive date or death date is considered as the resolution date.
 - If the day and month are missing or a date is completely missing, it will be considered as missing.
- Missing and partial non-study medication domain dates will be imputed using the derivation algorithm described in 4.1.3 of BMS Non-Study Medication Domain Requirements Specification¹⁸.
- Missing and partial radiotherapy and surgery dates will be imputed using algorithm described in [APPENDIX 2](#).
- For death dates, the following conventions will be used for imputing partial dates:
 - If only the day of the month is missing, the 1st of the month will be used to replace the missing day. The imputed date will be compared to the last known alive date and the maximum will be considered as the death date.
 - If the month or the year is missing, the death date will be imputed as the last known alive date.
 - If the date is completely missing but the reason for death is present, the death date will be imputed as the last known date alive.

- For date of recurrence after start of study therapy, the following conventions will be used for imputing partial dates:
 - If only the day of the month is missing, the 1st of the month will be used to replace the missing day. In case of the date of death is present and complete, the imputed recurrence date will be compared to the date of death. The minimum of the imputed recurrence date and date of death will be considered as the date of recurrence.
 - If the day and month are missing or a date is completely missing, it will be considered as missing.
- For date of recurrence to prior therapies, the following conventions will be used for imputing partial dates:
 - If only the day of the month is missing, the 1st of the month will be used to replace the missing day.
 - If the day and month are missing or a date is completely missing, it will be considered as missing.
- For other partial/missing dates, the following conventions were used:
 - If only the day of the month is missing, the 15th of the month will be used to replace the missing day.
 - If both the day and the month are missing, “July 1” will be used to replace the missing information.
 - If a date is completely missing, it will be considered as missing.

The following conversion factors will be used to convert days to months or years:

$$1 \text{ month} = 30.4375 \text{ days and } 1 \text{ year} = 365.25 \text{ days.}$$

Duration (e.g. time-to onset, time-to resolution) will be calculated as follows:

$$\text{Duration} = (\text{Last date} - \text{first date} + 1)$$

Last known alive date will be defined based on all appropriate dates collected on the CRF.

All statistical analyses will be carried out using SAS (Statistical Analysis System software, SAS Institute, North Carolina, USA) unless otherwise noted.

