3.6.1 Withdrawal of Consent

Subjects who request to discontinue study drug will remain in the study and must continue to be followed for protocol specified follow-up procedures. The only exception to this is when a subject

specifically withdraws consent for any further contact with him/her or persons previously authorized by subject to provide this information. Subjects should notify the investigator of the decision to withdraw consent from future follow-up **in writing**, whenever possible. The withdrawal of consent should be explained in detail in the medical records by the investigator, as to whether the withdrawal is from further treatment with study drug only or also from study procedures and/or post treatment study follow-up, and entered on the appropriate CRF page. In the event that vital status (whether the subject is alive or dead) is being measured, publicly available information should be used to determine vital status only as appropriately directed in accordance with local law.

3.6.2 *Lost to Follow-Up*

All reasonable efforts must be made to locate subjects to determine and report their ongoing status. This includes follow-up with persons authorized by the subject as noted above. Lost to follow-up is defined by the inability to reach the subject after a minimum of three documented phone calls, faxes, or emails as well as lack of response by subject to one registered mail letter. All attempts should be documented in the subject's medical records. If it is determined that the subject has died, the site will use permissible local methods to obtain the date and cause of death.

If investigator's use of third-party representative to assist in the follow-up portion of the study has been included in the subject's informed consent, then the investigator may use a Sponsor-retained third-party representative to assist site staff with obtaining subject's contact information or other public vital status data necessary to complete the follow-up portion of the study. The site staff and representative will consult publicly available sources, such as public health registries and databases, in order to obtain updated contact information. If after all attempts, the subject remains lost to follow-up, then the last known alive date as determined by the investigator should be reported and documented in the subject's medical records.

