8.3 Endpoints

8.3.1 Primary Endpoint

Disease-free survival is the primary endpoint of this study. Disease-free survival is the time between randomization date and first date of recurrence or death, whichever occurs first. Recurrence is defined as the appearance of one or more new lesions, which can be local, regional, or distant in location from the primary resected site (by imaging or pathology). DFS will be programmatically determined based on the disease recurrence date provided by the investigator. All deaths without prior recurrence will be included as DFS event - regardless of cause or of how long it has been since the last known disease evaluation. For subjects who remain alive and without recurrence, DFS will be censored on the date of last evaluable disease assessment.

Detailed censoring rules for the primary definition of DFS are presented in Table 8.3.1-1. (Sensitivity analyses of DFS will be described in the Statistical Analysis Plan [SAP]).

Table 8.3.1-1: Censoring Scheme Used in the Primary Definition of DFS

Situation	Date of Event or Censoring	Outcome
Recurrence ^{a,c}	Date of first recurrence	Event
Death ^{b,c} without recurrence	Date of death	Event
No baseline disease assessment	Date of randomization	Censored
No on-study disease assessments and no death	Date of randomization	Censored
No recurrence and no death	Date of last evaluable disease assessment	Censored
New anticancer therapy, tumor-directed radiotherapy, or tumor-directed surgery received without recurrence reported prior to or on the same day of disease assessment	Date of last evaluable disease assessment prior to or on the same date of initiation of subsequent therapy	Censored
Second non-esophageal and non-GEJ primary cancer reported prior to or on the same day of disease assessment	Date of last evaluable disease assessment prior to or on the same date of diagnosis of second non-esophageal and non-GEJ primary cancer	Censored

^a recurrence = appearance of one or more new lesions, which can be local, regional, or distant in location from the primary resected site

^b All deaths will be included as DFS event - regardless of cause or of how long it has been since the last known disease evaluation.

^c Without receiving preceding new anticancer therapy, tumor-directed radiotherapy, or tumor-directed surgery

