4 ENDPOINTS

4.1 Efficacy Endpoints

4.1.1 Disease Free Survival

DFS is the primary endpoint.

Disease-Free Survival is time between randomization date and first date of recurrence or death, whichever occurs first. Recurrence is defined as the appearance of one or more new lesions, which can be local, regional, or distant in location from the primary resected site (by imaging or pathology). DFS will be programmatically determined based on the disease recurrence date provided by the investigator. For subjects who remain alive and without recurrence, DFS will be censored on the date of last evaluable disease assessment. The on-study disease assessment considers CT scan, MRI and biopsy

Detailed censoring rules for the primary definition of DFS are presented in Table 4.1.1-1; graphical display is presented in [Figure 2](#).

Table 4.1.1-1: Censoring Scheme Used in the Primary Definition of DFS

[figure not shown]
Situation	Date of Event or Censoring	Outcome
Recurrence (a) (c) (d) (e)	Date of first recurrence	Event
Death (b) (c) (d) without recurrence	Date of death	Event
No baseline disease assessment	Date of randomization	Censored
No on-study disease assessments and no death (d)	Date of randomization	Censored
Death with prior subsequent therapies or second non-esophageal and non-GEJ primary cancer (d)	Date of randomization	Censored
No recurrence and no death (d) (e)	Date of last evaluable disease assessment	Censored
New anticancer therapy, tumor-directed radiotherapy, or tumor-directed surgery received or the second non-esophageal and non-GEJ primary cancer date without recurrence or death reported prior to or on the same day of disease assessment (d) (e)	Date of last evaluable disease assessment prior to or on the same date of initiation of subsequent therapy or the second non-esophageal and non-GEJ primary cancer date whichever is earlier	Censored

Table 4.1.1-1: Censoring Scheme Used in the Primary Definition of DFS

(a) recurrence = appearance of one or more new lesions, which can be local, regional, or distant in location from the primary resected site
(b) All deaths will be included as DFS event - regardless of cause or of how long it has been since the last known disease evaluation.
(c) Without receiving preceding new anticancer therapy, tumor-directed radiotherapy, tumor-directed surgery, or second non-esophageal and non-GEJ primary cancer.
(d) Without baseline disease.
(e) With on-study disease assessment.

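### SAP Section 8 discards a recorded year for partial death and recurrence dates, the two dates that drive DFS and OS, although it keeps the year for other dates

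*SAP*

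**What the plan says.** **Death dates (SAP Section 8).** If only the day is missing, the 1st of the month is used, and then "The imputed date will be compared to the last known alive date and the maximum will be considered as the death date". If more is missing, the rule is "If the month or the year is missing, the death date will be imputed as the last known alive date".

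**On-study recurrence dates (SAP Section 8).** If only the day is missing, the 1st of the month is used, capped at the date of death. Otherwise: "If the day and month are missing or a date is completely missing, it will be considered as missing".

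**How DFS is built.** Protocol Section 8.3.1 states that "DFS will be programmatically determined based on the disease recurrence date provided by the investigator", and SAP Section 4.1.1 repeats this. For those with no event, "For subjects who remain alive and without recurrence, DFS will be censored on the date of last evaluable disease assessment". When new therapy starts with no recurrence on record, SAP Table 4.1.1-1 censors at "Date of last evaluable disease assessment prior to or on the same date of initiation of subsequent therapy". Its footnote (c) counts a recurrence or death only if no new therapy and no second primary cancer came before it.

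**Other year-only dates.** The catch-all rule in SAP Section 8 uses 1 July of the recorded year. Appendix 2 dates year-only procedures and subsequent surgery at the later of 1 January of the recorded year and first dose. Both keep the year.

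**The concern.** The SAP uses whatever part of a date is recorded for day-missing deaths, for procedures, for surgery and for miscellaneous dates. It throws away a recorded year for only a few date types, and two of these define the efficacy endpoints.

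For death, the result can be a date that the data themselves rule out. For recurrence, the SAP blanks the date and does not say what becomes of a recurrence that was reported but has no usable date. Since DFS is derived from that date, a programmer following the text has nothing to enter as an event. At stake are the timing of some OS and DFS events and the status of some DFS events, which would have to be settled case by case if the text stays silent.

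The setting is not purely theoretical. Protocol Sections 3.6.1 and 3.6.2 allow public sources for subjects who have withdrawn or cannot be reached: "publicly available information should be used to determine vital status only as appropriately directed in accordance with local law".

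**Working it through.** **1. The plan's own figure, used only to gauge size.** Inputs from SAP Section 5.3: 440 DFS events, average HR 0.72, 2:1 allocation, two-sided alpha 0.05, stated power about 91%. By the Schoenfeld formula, power = Φ(√(D·p(1−p))·|ln HR| − 1.96), with p = 1/3:

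- √(440 × 2/9) = 9.888; |ln 0.72| = 0.3285; product 3.248; minus 1.96 = 1.288; Φ = 90.1%. This agrees with the stated figure to within one percentage point.

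**2. Death, month missing, year known.** Assumed example: randomized 1 June 2017, last known alive 15 November 2018, death recorded as 2019 only. With duration = last date − first date + 1 and 30.4375 days per month (SAP Section 8):

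| Date used | Days | OS (months) |
|---|---|---|
| SAP rule, 15 Nov 2018 | 533 | 17.5 |
| Earliest date the record allows, 1 Jan 2019 | 580 | 19.1 |
| Latest date the record allows, 31 Dec 2019 | 944 | 31.0 |

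The SAP date is 47 to 411 days too early and lies in a year that the record excludes. The later of 1 January 2019 and the last known alive date gives 19.1 months and cannot conflict with the record. If last contact falls in the recorded year of death, that rule and the SAP rule give the same date.

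**3. How often a year-only death would be contradicted.** Assume death is uniform over the year and the gap since last contact is uniform from 0 to G days. For G up to 365, P(last contact in an earlier year) = G/(2 × 365):

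- G = 91 (the 3-month contact schedule, SAP Section 2.1): 12%
- G = 105: 14%
- G = 182: 25%
- G = 365: 50%

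The share of deaths with a year only is not in the documents. Assuming 0.5-2% of the 460 planned deaths gives 2.3 to 9.2. Multiplying, 2.3 × 0.125 = 0.3 and 9.2 × 0.50 = 4.6, so roughly 0.3 to 4.6 deaths would change date. None is lost as an OS event.

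**4. Recurrence, year only, traced through SAP Table 4.1.1-1.** With the recurrence date missing:

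- Alive, no new therapy: censored at the last evaluable assessment. The event is not counted.
- New therapy follows: censored at or before that therapy, and footnote (c) excludes a later death. The event is not counted in the primary definition.
- Death follows without new therapy or a second primary cancer: the death counts, so the event is kept but moved to the death date.

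An awkward combination follows. If a recurrence and a subsequent tumor-directed surgery are both known only by year, Appendix 2 keeps a date for the surgery, which triggers censoring, while Section 8 discards the date of the recurrence, which would have been the event.

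**5. Size for DFS.** Repeating step 1 with fewer events: 435 gives 89.8%, 430 gives 89.5%, 420 gives 88.8%. The final DFS analysis is triggered by at least 440 observed events (SAP Section 5.4), so uncounted events would mainly delay it and distort some DFS times rather than reduce power.

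**The case against.** - **The SAP blanks a date, not an event.** A reader might infer that the plan deletes documented recurrences. The text does not say so. Non-counting is the programmed consequence of deriving DFS from a missing date, and it presumes that the CRF accepts a year-only recurrence date; the CRF is not among the documents. This limits the wording. It does not close the gap, because no rule covers a reported but undated recurrence.
- **Year-only recurrences should be very rare.** Recurrence takes the date of the first imaging or pathology that showed it (Protocol Section 5.4.3). This stands.
- **Not every such case loses an event.** A reader might infer that each year-only recurrence costs one of the 440 events and the later death too. A subject contributes at most one DFS event, and a death with no intervening therapy or second primary cancer still counts.
- **Sensitivity analyses help in part.** SAP Section 7.5.2.1 plans a DFS analysis without truncation at subsequent therapy, which recovers a later death but not the undated recurrence. Another counts recurrence-free subjects lost to follow-up as events, which reaches only that group. Neither addresses partial dates.
- **Large OS errors are unlikely.** A reader might picture last contact in March 2019 and a death recorded as 2022, at least 33 months too early. The rule permits this, but it is a worst case. Survival contact is every 3 months, the sponsor may request extra survival sweeps (Protocol Section 3.6), and sites must seek the date of death by permissible local methods (Protocol Section 3.6.2). That public sources more often give partial dates is inference and is not in the documents.
- **The conventions are permissive.** Section 8 opens with "The following conventions may be used for imputing partial dates for analyses requiring dates". However, the death and recurrence bullets are worded as rules that will apply, and no alternative is offered.

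**Conclusion.** The point holds as a small, real defect in SAP Section 8. The death rule gives a date that contradicts the record whenever the year of death is known, the month is not, and last contact was in an earlier year. The conflict is with the recorded year; no negative or otherwise undefined survival time arises. The recurrence rule leaves the DFS status of a year-only recurrence to the consequences of a missing date: not counted, or postponed to death.

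The numerical effect is likely small. The figure of 0.3 to 4.6 deaths rests on an assumed 0.5-2% share of year-only deaths and assumed uniform contact gaps of up to 91 to 365 days. For year-only recurrences the documents support no frequency at all; even 10 uncounted events would move DFS power by only about 0.6 points. A reader might also infer bias in favour of one arm. Nothing in the documents shows a direction, and the trial is double-blind. The reason to act is that the repair is nearly free and removes ad hoc decisions about primary events.

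**What to change.** In SAP Section 8:

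1. **Death, year known, month missing:** use the later of 1 January of the recorded year and the last known alive date. Keep the present rule when the year is also missing.
2. **Reported on-study recurrence, year only:** count it as a DFS event dated within the recorded year, no earlier than the day after the last recurrence-free assessment, and no later than death or the start of therapy for that recurrence.
3. **Reporting:** list all year-only death and recurrence dates by arm. Add a sensitivity check that moves the imputed recurrence date to the earliest and then the latest date in its admissible window.

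An optional refinement is to floor a day-missing recurrence at the day after the last recurrence-free assessment; the shift is at most about 30 days.

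The cost is a few lines of text, the matching programming and one listing. No new data are needed.

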9 DOCUMENT HISTORY

Table 9-1: Document History

Version Number	Author(s)	Description
1.0 Apr 25, 2017		Original Issue based on revised protocol 01 dated Aug 24, 2016

Table 9-1: Document History

[figure not shown]
[figure not shown]

2.0 Oct 24, 2019
		
Based on revised protocol 03 dated June 06, 2019. The following changes are made in the SAP amendment to reflect the protocol amendment of having DFS as the primary endpoint, and OS as the secondary endpoint.  .
 
 • Objectives and endpoints to keep DFS as the sole primary endpoint and change OS to the secondary endpoint • Sample size and power • Schedule of analyses • The method to maintain blinding of OS if not positive at two interim looks of the studyThe method for alpha spending between IA and FA for DFS and OS PFS2 definition and analyses 
The SAP amendment also incorporates the IO core SAP.

3.0 May 4, 2020
		
Minor updates from SAP version 2.0 to add sensitivity analyses in Section 7.5.2.1 and other minor edits. Details are summarized below.
 
 • • Remove dose reduction in Section 7.6.4 as it is not applicable in this study. • Include in 7.5.2.2 Consistency of Treatment Effect in Subsets, Pathologic tumor status (ypT0, ypT1/ypT2, ypT3/ypT4, unknown) • Remove cumulative plot of baseline PD-L1 expression in section 7.8 as it is not very informative. • Remove the log-rank test and keep the Cox model for the subgroup analysis by PD-L1 status in section 7.8. • Add "c) no on-study disease assessment but death with prior subsequent therapy or second primary cancer" for censored on randomization date in section 7.5.2

4.0 Sept 30, 2020
		
Minor format update on hyperlinks, references, and page numbers. Correction of the relative dose intensity formula in Table 7.4-1 Administration of study therapy: definition of parameters.

Table 9-1: Document History

--	--	--

APPENDIX 1 TIME-TO ONSET AND TIME-TO RESOLUTION DEFINITION AND CONVENTIONS FOR SELECT ADVERSE EVENTS, IMMUNE-MEDIATED ADVERSE EVENTS AND EVENTS OF SPECIAL INTEREST

Time-to onset definition

Time-to onset of AE (any grade) for a specific category is defined as the time between the day of the first dose of study treatment and the onset date of the earliest AE (of any grade) in this category.

The time-to onset of AE (grade 3-5) for a specific category is defined similarly with an onset date corresponding to a grade 3-5 AE.

Time-to onset of drug-related AE (any grade or grade 3-5) for a specific category is defined similarly but restricted to drug-related AE.

Time-to onset for a specific subcategory is defined similarly but restricted to event of this subcategory.

Time-to resolution definition

In order to derive the time-to resolution, overlapping or contiguous AEs within a specific category or subcategory will be collapsed into what will be termed “clustered” AEs. For example, if a subject (without pre-treatment AE) experienced an AE from 1st to 5th January, another AE (with different PT but within same category) from 6th to 11th January and same AE from 10th to 12th January, these will be collapsed into one clustered AE from 1st to 12th January. [Table 9-2](#) is summarizing key derivation steps for each type of clustered AEs.

Time-to resolution of AE (any grade) for a specific category is defined as the longest time from onset to complete resolution or improvement to the grade at baseline among all clustered AEs experienced by the subject in this category per adverse event criteria category. Events which worsened into grade 5 events (death) or have a resolution date equal to the date of death are considered unresolved. If a clustered AE is considered as unresolved, the resolution date will be censored to the last known alive date. Improvement to the grade at baseline implies that all different events in the clustered adverse event should at least have improved to the corresponding (i.e. with same preferred term) baseline grade. This measure is defined only for subjects who experienced at least one AE in the specific category.

The time-to resolution of AE (grade 3-5) for a specific category is defined similarly with an onset date corresponding to a grade 3-5 AE.

Time-to resolution of drug-related AE (any grade or grade 3-5) for a specific category is defined similarly but restricted to drug-related AE.

The time-to resolution of AE (any grade or grade 3-5, drug-related or all) where immune modulating medication was initiated is defined similarly. For data presentation not restricted to IMAE, the additional condition that the subject started an immune modulating medication during the longest AE resolution period will be applied.

Time-to resolution for a specific subcategory is defined similarly but restricted to event of this subcategory.

Table 9-2: Derivation of clustered AE

Type of clustered AE	Derivation
Any grade	Collapse any on-treatment AE from the same category
Drug-related of any grade	Collapse any on-treatment drug-related AE from the same category
Grade 3-5	Collapse any on-treatment AE from the same category. Resolution will be based on the onset date of the earliest grade 3-5 records (if no grade 3-5 record, clustered AE is excluded)
Drug-related of Grade 3-5	Collapse any on-treatment drug-related AE from the same category Resolution will be based on the onset date of the earliest grade 3-5 record (if no Grade 3-5 record, clustered AE is excluded)

The algorithm for collapsing adverse event records is using the following conventions:

For each subject and specified category, the corresponding adverse event records will be collapsed when:

- 1) Multiple adverse event records have the same onset date.
- 2) The onset date of an event record is either the same day or 1 day later than the resolution date of a preceding event record (contiguous events).
- 3) The onset date of an event record is after the onset date and prior to or on the resolution date of a preceding event record (overlapping events).

